2 STUDY DESIGN

2.1 STUDY DESIGN OVERVIEW

This is a single-arm, multi-center, prospective clinical study. The study will be conducted in 6-12 clinical study sites in the United States. The study is expected to enroll up to 80 children, aged 2-5.9 in order to obtain 60 evaluable subjects. Subjects will be considered evaluable if they have at least 8 weeks of data during Phase 2 of hybrid closed-loop.

2.2 INVESTIGATIONAL DEVICE

The Omnipod Horizon[™] Automated Glucose Control System ("Horizon[™] System") is comprised of three primary components:

- Omnipod Horizon[™] tubeless, insulin delivery alternate controller enabled (ACE) pump (Pod) with the Horizon[™] algorithm
- Omnipod Horizon[™] Personal Diabetes Manager (PDM) which is a Samsung J3 locked down Android device that operates the Omnipod Horizon[™] App
- Dexcom G6 Continuous Glucose Monitoring (CGM) system

In addition, the following non-investigational, commercially available devices will be used during the study:

- Contour[®] Next One blood glucose meter (Ascensia Diabetes Care, [name])
- Precision Xtra ketone meter (Abbott Diabetes Care Inc., [name])

2.3 STUDY SCHEDULE

The study will consist of a 14-day outpatient standard therapy (ST) outpatient phase (Phase 1), a 13-week outpatient hybrid closed-loop (HCL) phase (Phase 2), and a 6-month hybrid closed-loop extension phase (Phase 3). The sponsor intends to submit results from Phase 2 for marketing clearance after data collection for Phase 2 is complete.

The Horizon[™] System has two modes. In Manual Mode, the system will function equivalently to the Omnipod DASH System. This includes delivering insulin at programmed basal rates and bolus amounts with the option to set temporary basal profiles. In Automated Mode, the system will support the use of multiple target glucose values. The

Statistical Analysis Plan

programmed basal rates, glucose targets and bolus calculator settings will inform the MPC (model predictive control) algorithm for insulin dosing parameters.

2.4 STUDY SUCCESS

The study will be deemed successful if the incidence rates of severe hypoglycemia and diabetic ketoacidosis during Phase 2 are considered acceptable compared to published rates.

2.5 RANDOMIZATION

This is a single-arm, multicenter, prospective clinical study where all eligible subjects will use the investigation device. Subjects will not be randomized.

2.6 POINT OF ENROLLMENT

A subject is enrolled in the study upon placement of the first study CGM. Subjects who do not meet the eligibility criteria will not continue in the study and will be considered screen failures.

3 STUDY OBJECTIVES AND ENDPOINTS

3.1 SAFETY OBJECTIVE AND ENDPOINTS

The safety objective is to evaluate the safety of the Omnipod Horizon[™] Automated Glucose Control System in preschool patients with type 1 diabetes. The safety objective will be evaluated by summarizing the following events during Phase 2:

- Incidence rate of severe hypoglycemia (events per person months)
- Incidence rate of diabetic ketoacidosis (DKA) (events per person months)

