6.1.1 Primary Safety Endpoints

The primary safety objective will be evaluated by summarizing the following events during Phase 2, and separately during Phase 3

- Incidence rate of severe hypoglycemia (events per person months)
- Incidence rate of diabetic ketoacidosis (DKA) (events per person months)

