9.9 Visit 13 (End of Phase 2)

Visit 13 will be conducted either over the telephone or in person at the clinical study site on Study Day 94 ± 3 days. This visit will include:

- A1C (blood draw sent to NGSP laboratory)
- Review of concomitant medications
- Height (if visit is conducted in person at the clinical site)
- Weight (if visit is conducted in person at the clinical site)
- Assessment of vital signs (if visit is conducted in person at the clinical site)
- Assessment of AEs since last visit
- Completion of questionnaires (See Table 2: Questionnaires for specific requirements by age group):
 - WHO-5
 - DTSQc Parent
 - P-PAID-Child
 - Hypoglycemia Confidence Scale
 - PSQI
 - IDSS (T1)
 - SUS
 - INSPIRE-Parent
 - Used to measure a caregiver's experience of the support they receive
 - Clarke Questionnaire
 - Human Factors (HF) Questionnaire
 - Measures trust in the Horizon System
- Discontinuation of Horizon Data Portal monitoring if not continuing into Phase 3
- Return study devices if not continuing into Phase 3 (Omnipod Horizon™ System, CGM, BG and ketone meters) if not participating in the extension phase
- Complaints/device deficiencies such as occlusion alarms and system hazard alarms since last visit
- Device uploads for BG and ketone meter
- Data review of Automated Mode use by clinician
- Assessment of activity and routine carb consumption

This visit will mark the discontinuation of Phase 2 and mark the end of the study for subjects not continuing to Phase 3.

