Visit 15 will be conducted either over the telephone or in person at the clinical study site on Study Day 150 ± 5 days. This visit will include:

- Review of concomitant medications
- Assessment of AEs since last visit
- Complaints/device deficiencies such as occlusion alarms and system hazard alarms since last visit
- Device uploads for BG and ketone meter (if visit is conducted at the clinical site)
- Data review of Automated Mode use by clinician

10.3 Visit 16

Visit 16 will be conducted either over the telephone or in person at the clinical study site on Study Day 180 ± 5 days. This visit will include:

- A1C (blood sample sent to NGSP laboratory)
- Review of concomitant medications
- Assessment of AEs since last visit
- Complaints/device deficiencies such as occlusion alarms and system hazard alarms since last visit

- Device uploads for BG and ketone meter (if visit is conducted at the clinical site)
- Data review of Automated Mode use by clinician

10.4 Visits 17 and 18

Visits 17 and 18 will be conducted either over the telephone or in person at the clinical study site on Study Day 210 \pm 5 days and Study Day 240 \pm 5 days, respectively. These visits will include:

- Review of concomitant medications
- Assessment of AEs since last visit
- Complaints/device deficiencies such as occlusion alarms and system hazard alarms since last visit
- Device uploads for BG and ketone meter (if visit is conducted at the clinical site)
- Data review of Automated Mode use by clinician

10.5 Visit 19

Visit 19 will be conducted either over the telephone or in person at the clinical study site on Study Day 270 \pm 5 days. This visit will include:

- A1C (blood sample sent to NGSP laboratory)
- Informed Consent (consent for second 6-month interval of Phase 3 may occur on or any time before this visit)
- Review of concomitant medications
- Assessment of AEs since last visit
- Complaints/device deficiencies such as occlusion alarms and system hazard alarms since last visit
- Device uploads for BG and ketone meter (if visit is conducted at the clinical site)
- Data review of Automated Mode use by clinician

10.6 Visit 20

Visit 20 will be conducted either over the telephone or in person at the clinical study site on Study Day 315 \pm 5 days. This visit will include:

- Review of concomitant medications
- Assessment of AEs since previous visit
- Complaints/device deficiencies such as occlusion alarms and system hazard alarms since last visit

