- Device uploads for BG and ketone meter (if visit is conducted at the clinical site)
- Data review of Automated Mode use by clinician

10.7 Visit 21

Visit 21 will be conducted either over the telephone or in person at the clinical study site on Study Day 360 \pm 5 days. This visit will include:

- A1C (blood sample sent to NGSP laboratory)
- Review of concomitant medications
- Assessment of AEs since previous visit
- Complaints/device deficiencies such as occlusion alarms and system hazard alarms since last visit
- Device uploads for BG and ketone meter (if visit is conducted at the clinical site)
- Data review of Automated Mode use by clinician

10.8 Visit 22

Visit 22 will be conducted either over the telephone or in person at the clinical study site on Study Day 405 \pm 5 days. This visit will include:

- Review of concomitant medications
- Assessment of AEs since previous visit
- Complaints/device deficiencies such as occlusion alarms and system hazard alarms since last visit
- Device uploads for BG and ketone meter (if visit is conducted at the clinical site)
- Data review of Automated Mode use by clinician

10.9 Visits 23

Visits 23 will be conducted either over the telephone or in person at the clinical study site on Study Day 450 \pm 5 days. This visit will include:

- A1C (blood sample sent to NGSP laboratory)
- Informed Consent (consent for extension in study through commercial availability of the Omnipod 5 System may occur on or any time before this visit)
- Review of concomitant medications
- Height
- Weight
- Assessment of AEs since previous visit
- Return study devices (Omnipod Horizon™ System, CGM, BG and ketone meters) if this visit marks the Study Exit
- Complaints/device deficiencies such as occlusion alarms and system hazard alarms since last visit
- Device uploads for BG and ketone meter
- Data review of Automated Mode use by clinician

Subjects continuing in the study after Visit 23 will continue in the study through commercialization. Subjects will complete their final study visit at their next study visit

once commercially available. Therefore, subjects may complete the study at different visits depending on the timing of their visit in relation to commercialization.

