12.7 Stopping Criteria

12.7.1 Participant Discontinuation of Study Participation

In the case of a UADE, the Medical Monitor will determine if the use of the study device will be suspended while the problem is diagnosed. The use of the study device may continue if the Medical Monitor believes the event is explainable, unlikely to reoccur and that it is safe for the subject to continue using the device. Alternately, the Medical Monitor may request the study subject, or all study subjects, to stop using the study device or to only use in Manual Mode. Should all study subjects be required to stop using the study device or to only use in Manual Mode due an UADE, use of the study device or Automated Mode will not be restarted until approval is received from the IRB, DSMB and FDA.

Use of the study device by a participant will be discontinued if any of the following occur:

- The investigator believes it is unsafe for the participant to continue on the intervention. This could be due to the development of a new medical condition or worsening of an existing condition; or participant behavior contrary to the indications for use of the device that imposes on the participant’s safety.
- The participant requests that the treatment be stopped
- Participant pregnancy
- One distinct episode of DKA as defined above
- One distinct severe hypoglycemia events as defined above

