1 PURPOSE

The purpose of this Statistical Analysis Plan (SAP) is to describe the statistical methodology that will be used to confirm the safety and effectiveness of the Omnipod Horizon[™] Automated Glucose Control System in children with type 1 diabetes aged 2.0-5.9 years. Should there be any discrepancy between the preschool study protocol and this SAP, the content of the SAP shall prevail.

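### The governing SAP omits the Phase 3 severe hypoglycemia and DKA rates that the protocol makes primary safety endpoints, leaving 65% to 79% of per-child device time outside any planned rate

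*SAP*

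**What the plan says.** Protocol 6.1.1 reads: "The primary safety objective will be evaluated by summarizing the following events during Phase 2, and separately during Phase 3". The two events are severe hypoglycemia and DKA, each as a rate per person-month. Protocol 13.1.1.1 and the protocol summary say the same.

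SAP 3.1 names the same two rates but limits them: "The safety objective will be evaluated by summarizing the following events during Phase 2". On conflicts, SAP 1 says: "Should there be any discrepancy between the preschool study protocol and this SAP, the content of the SAP shall prevail". Protocol 13.10 agrees.

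Other provisions that bear on the point:

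- **Phase 3 elsewhere in the SAP.** SAP 3.3 carries Phase 3 for A1C, CGM metrics, time in closed loop, GMI, insulin and BMI. SAP 7.1 says all available data will be used for Phase 3 endpoints.
- **Adverse events.** SAP 5.4 tabulates all adverse events by study phase and lists them. The tables give the number and percentage of subjects, with a repeated event counted once per child.
- **Safety set.** SAP 7.1.2 makes mITT (everyone who enters hybrid closed-loop) the primary set for the safety endpoints.
- **Length of Phase 3.** SAP 2.3 gives six months and SAP 6.6 takes Visit 19 as its end. The protocol runs to Visit 23 and on to commercial availability.
- **Discontinuation.** Under Protocol 12.7.1, device use stops after "One distinct episode of DKA as defined above" or after one severe hypoglycemia event. The protocol summary opens Phase 3 to children who complete Phase 2.

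**The concern.** A rate that the protocol lists among its primary safety endpoints has no planned analysis in the document that governs. A Phase 2-only scope for the SAP does not explain this, because the SAP plans Phase 3 analyses for the effectiveness measures. Only the safety rates lose the later phase.

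Severe hypoglycemia and DKA are rare, and about 13 weeks in 60 to 80 children says little about a rare rate. Most of the information on these events will come from the extension, which is the part the governing rate endpoint leaves out.

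The protocol's separate Phase 3 rate also needs care in reading. A child whose device use ended after an event in Phase 2 adds no device time to Phase 3, so that rate comes from children who got through Phase 2 without one.

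**Working it through.** **Inputs**

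- Hybrid closed-loop starts on Day 1 (Protocol 9.2). Visit 13 is Day 94 (9.9), Visit 19 is Day 270 (10.5) and Visit 23 is Day 450 (10.9).
- N is 60 evaluable to 80 enrolled (Protocol 5.2, SAP 2.1). The primary safety set is mITT, so N may exceed 60.
- Continuation into Phase 3 is not given. I assume 100%, with 60% as a sensitivity case. Dropout within a phase is ignored.
- One month is 30.4375 days.

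**Check against a stated figure.** Day 450 / 30.4375 = 14.8 months. The protocol puts Visit 23 at about 15 months, so the visit days reproduce it. Neither document gives an expected event count or precision for the safety rates.

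**Share of device time left out**

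- To Day 270: Phase 2 is 93 of 269 days = 35%, so 65% is left out.
- To Day 450: Phase 2 is 93 of 449 days = 21%, so 79% is left out.

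**Upper limit with zero events.** Person-months T = N × [93 + c × (D − 93)] / 30.4375, where c is the fraction continuing and D is 93, 269 or 449 days. The exact two-sided 95% Poisson upper limit is −ln(0.025)/T = 3.689/T per person-month. Multiplying by 1200 gives events per 100 person-years.

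| Exposure | N | c | T (person-months) | Upper limit per 100 person-years |
|---|---|---|---|---|
| Phase 2 only | 60 | – | 183.3 | 24.1 |
| Phase 2 only | 80 | – | 244.4 | 18.1 |
| Phases 2+3 to Day 270 | 60 | 100% | 530.3 | 8.3 |
| Phases 2+3 to Day 270 | 60 | 60% | 391.5 | 11.3 |
| Phases 2+3 to Day 270 | 80 | 100% | 707.0 | 6.3 |
| Phases 2+3 to Day 450 | 60 | 100% | 885.1 | 5.0 |
| Phases 2+3 to Day 450 | 60 | 60% | 604.4 | 7.3 |
| Phases 2+3 to Day 450 | 80 | 100% | 1180.1 | 3.8 |

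For N = 60 the pooled limit is 24.1/11.3 = 2.1 to 24.1/5.0 = 4.8 times tighter.

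**Comparison with Protocol Table 5.** For children under 18, Table 5 gives 4-5% with severe hypoglycemia and 3-4% with DKA, with no recall period. Read as annual, 3-5% converts by −ln(1 − p) to about 3.0-5.1 per 100 person-years, and only the pooled limit comes near it. Read as three-monthly, it is about 12-21 per 100 person-years. Phase 2 alone with N = 80 and no events (18.1) is then below only the top of that range.

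**Selection into Phase 3.** Let λ be the summed monthly hazard of the two events, from Table 5. Let children's risks vary as a gamma frailty with mean 1 and variance θ. Then S(t) = (1 + θλt)^(−1/θ), and the first-event rate over (a, b) is [S(a) − S(b)] / ∫S(t)dt from a to b.

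- Children expected to stop the device in Phase 2 for either event, at a common hazard: 1.1 to 1.9 of 60-80 (annual reading), or 4.2 to 7.2 (three-monthly reading).
- θ = 0, one common constant hazard: Phase 3 rate / Phase 2 rate = 1.00, so no effect.
- θ = 1 to 5, annual reading: ratio 0.975 to 0.797, so the Phase 3 rate is 3% to 20% lower.
- θ = 1 to 5, three-monthly reading: ratio 0.909 to 0.547, so 9% to 45% lower.
- The pooled rate is 3% to 47% below the initial hazard over the same settings. Pooling improves precision but does not remove the depletion.

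The values of θ are assumptions; the documents give none.

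**The case against.** The strongest reply is that the staging is deliberate. Phase 2 is to be submitted for clearance once its data collection is complete, Phase 3 results go in separately, and study success is tied to Phase 2 rates in both documents (Protocol 13.2, SAP 2.4). A pooled rate could not serve that submission. This stands, and the success decision is unaffected. It does not explain why the SAP plans Phase 3 analyses of A1C, CGM, insulin and BMI but not of the safety rates.

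A reader might infer that Phase 3 events are lost. They are not: SAP 5.4 tabulates them by phase and lists them, the Medical Monitor adjudicates them and the DSMB is informed. What is missing is the person-time rate and its limits.

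A reader might also infer that a Phase 3 rate must look lower because event-prone children have left. That requires risk to differ between children. Under one common constant hazard there is no effect, and the documents do not say how much risk varies. Nor is freedom from events a stated Phase 3 entry criterion; it follows from combining the discontinuation rule with entry of completers.

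Finally, it is tempting to count a full extra year of exposure. The governing SAP gives Phase 3 six months, and each extension interval needs its own consent (Protocol 10), so the gain may be nearer twofold than fivefold.

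**Conclusion.** The point holds as a conflict between the documents on a primary safety endpoint. As the governing text stands, the Phase 3 severe hypoglycemia and DKA rates required by Protocol 6.1.1 have no planned analysis, and most device time falls outside any planned rate whichever end of Phase 3 is used. Pooling would tighten the zero-event bound about two to five times for 60 children. That range depends on the end of Phase 3 and on continuation of 60% to 100%, and it ignores dropout within a phase.

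The selection issue is secondary and conditional: a stand-alone Phase 3 rate may read low if risk differs between children, by an amount the documents cannot fix. The consequence is for the safety endpoint that is reported and its precision, not for the success criterion.

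**What to change.** - In SAP 3.1 and 5.4, restore the Phase 3 severe hypoglycemia and DKA rates per person-month.
- Add a combined Phase 2 and 3 rate for each event, with person-time from Visit 4 to the end of device use and exact Poisson 95% limits. Add a time-to-first-event cumulative incidence over the same period.
- Beside the Phase 3 rate, show how many children stopped the device in Phase 2 because of these events.
- Reconcile the end of Phase 3 between the documents: Visit 19 in the SAP, Visit 23 and beyond in the protocol.

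Leave the Phase 2 success criterion and the staged submission as they are. The cost is SAP wording and one extra table, built from adverse event and exposure data already collected. No visits, patients or clinical rules change.

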3.2 PRIMARY EFFECTIVENESS OBJECTIVE AND ENDPOINTS

The primary effectiveness objective is to evaluate the effectiveness of the Omnipod Horizon[™] Automated Glucose Control System. The primary effectiveness objective will be evaluated by analyzing the following endpoints:

- A1C at the end of Phase 2 compared to baseline A1C
- Percentage of time in range (70-180 mg/dL) during Phase 2 of the hybrid closedloop phase compared to Phase 1 (standard therapy)

3.3 SECONDARY OBJECTIVE AND ENDPOINTS

The secondary objective is to evaluate additional glycemic measures of effectiveness of the Omnipod Horizon[™] Automated Glucose Control System. The secondary objective will be evaluated based on the following per subject endpoints *with* prespecified hypotheses:

- Glucose metrics from system CGM during the hybrid closed-loop phase for Phase 2 will be compared to Phase 1 overall:
 - Percentage of time in range > 180 mg/dL
 - Percentage of time in range < 70 mg/dL

Additional per subject endpoints *without* prespecified hypotheses used to evaluate the secondary objective include:

- A1C:
 - A1C at the end of Phase 2 (Visit 13), 6 months (Visit 16) and the end of Phase 3 (Visit 19)
 - Change from baseline in A1C at the end of Phase 2 (Visit 13), 6 months (Visit 16) and the end of Phase 3 (Visit 19)
 - Proportion of subjects demonstrating an improvement from baseline in A1C at the end of Phase 2 (Visit 13), 6 months (Visit 16) and the end of Phase 3 (Visit 19)
- Glucose metrics from system CGM during the hybrid closed-loop phase for Phase 2 and Phase 3 will be compared to Phase 1 during the day, overnight, and overall:
 - Mean glucose
 - Percentage of time in range 70-180 mg/dL
 - Percentage of time in range 70-140 mg/dL
 - Percentage of time in range > 180 mg/dL
 - Percentage of time in range ≥ 250 mg/dL
 - Percentage of time in range \geq 300 mg/dL
 - Percentage of time in range < 70 mg/dL
 - Percentage of time in range < 54 mg/dL
 - Standard deviation
 - Coefficient of variation
- Percentage of time in hybrid closed-loop as proportion of overall device usage time during Phase 2 and Phase 3
- Glucose management indicator (GMI) based on overall mean glucose during Phase 2 and Phase 3 will be compared to Phase 1
- Insulin requirements during Phase 2 and Phase 3 will be compared to Phase 1:
 - Total daily insulin (TDI) (units, units/kg)
 - Total daily basal insulin (units, units/kg)
 - Total daily bolus insulin (units, units/kg)
- Change from baseline in BMI (kg/m²) at end of Phase 2 and Phase 3

4 ANALYSIS OF PRIMARY EFFECTIVENESS ENDPOINTS

There are two primary effectiveness endpoints. The primary effectiveness objective will be evaluated using the following endpoints:

- A1C at the end of Phase 2 compared to baseline A1C
- Percentage of time in range (70-180 mg/dL) during Phase 2 of the hybrid closedloop phase compared to Phase 1 (standard therapy)

4.1 SAMPLE SIZE

This is a single-arm, multi-center, prospective study. The sample size and study duration were determined to allow for an adequate safety profile of the investigational device. The study will be claimed successful if the incidence rates of severe hypoglycemia and diabetic ketoacidosis are considered acceptable compared to published rates.

In addition, a statistically powered sample size was determined for the two primary effectiveness endpoints. Since each of the primary effectiveness endpoints will be evaluated separately, the significance level will be adjusted so that the overall type I error can be maintained at one-sided 2.5%, and each endpoint will be tested at one-sided 1.25%.

A1C

The sample size estimation is based on the following assumptions:

- Mean difference between paired observations of A1C at the end of Phase 2 compared to baseline is -0.5%
- Standard deviation of the difference between paired observations of A1C at the end of Phase 2 participation compared to baseline is 0.8%
- Power of 90% and one-sided significance level of 1.25%

The estimates for the mean difference and standard deviation of the difference between the paired observations were obtained from previous Omnipod studies, where subjects experienced a mean change in A1C of 0.38% over 3 months (standard pump therapy only), from 8.1 to 7.7%, n=85 (data on file). Based on the above assumptions, 35 subjects are required to provide evaluable data.

Percentage of Time in Range 70-180 mg/dL

The sample size estimation is based on the following assumptions:

 Mean difference between paired observations of percentage of time in range 70-180 mg/dL during Phase 2 of hybrid closed-loop compared to Phase 1 is 10%

- Standard deviation of the difference between paired observations of percentage of time in range 70-180 mg/dL during Phase 2 of hybrid closed-loop compared to Phase 1 is 10%
- Power of 90% and one-sided significance level of 1.25%

The estimates for the mean difference and standard deviation of the difference between the paired observations were obtained from recent Omnipod Horizon study, G170143, where twelve (12) subjects aged 3.4-5.9 years experienced a mean change in percentage of time in range 70-180 mg/dL of 13.2 \pm 10.2%. Based on the above assumptions, 11 subjects are required to provide evaluable data.

To gather adequate safety and effectiveness data on the performance of the Omnipod Horizon[™] System, the study plans to enroll up to 80 subjects to obtain a minimum of 60 evaluable subjects. Subjects will be enrolled across 6-12 clinical study sites. No single site should enroll more than 24 subjects.

